5.2 Exclusion criteria

- Patients with "do-not-resuscitate" orders
- Crash, awake or delayed sequence intubations
- Patients requiring non-invasive positive pressure ventilation
- Cardiac arrest
- Clinical suspicion or confirmed diagnosis of base of skull fractures or severe facial trauma that precludes nasal cannula placement

- Vulnerable patient populations (e.g. pregnant women, prisoners)

6. STUDY DEVICE

In the treatment group for pre- and apnoeic oxygenation using HFNC, the patients will be pre-oxygenated and oxygenated during apnoea with 60L/min of warm and humidified oxygen using the AIRVO™ 2 Humidifier with Integrated Flow Generator (Fisher & Paykel Healthcare, Auckland, New Zealand).

Figure 4. (a) Image of AIRVO™ 2 Humidifier with Integrated Flow Generator (left); (b) Nasal cannula interface (middle); and (c) heating tube (right).

Figure 5: Image showing how the nasal cannula will be connected to the AIRVO™ 2 system and patient.

7. STUDY PROCEDURES

Method of oxygenation for each patient will be dependent on the treatment combination randomised and assigned as described above.

Patients will be **pre-oxygenated for 3 minutes** with 60L/min using the AIRVO™ 2 Humidifier with Integrated Flow Generator **or** non-rebreather mask depending on treatment group randomised to. Premedication (if required) will be given 3 minutes prior to RSI, i.e. at the start of pre-oxygenation. Once 3 minutes of pre-oxygenation is completed, induction medications are administered and apnoeic oxygenation commenced as per assigned treatment group, which comprised of nasal cannula oxygenation at 15L/min **or** HFNC at 60L/min. Intubation attempts starts after 30 to 45 seconds (onset time of paralytic agent, typically succinylcholine or rocuronium). If the intubator is of resident grade, only 2 attempts are allowed before escalating to an EM specialist. Each attempt is defined as passage of laryngoscope through mouth.

End of intubation is defined as placement of endotracheal tube with confirmation of placement using quantitative end-tidal CO₂.

Clinical data collected (with no identifying data) will include:

(a) Pre-oxygenation	
• Time pre-oxygenation started• Position adopted for pre-oxygenation• Duration of pre-oxygenation (time of induction = end of pre-oxygenation)• SpO₂ at beginning and end of pre-oxygenation (i.e. prior to induction)• Mode of pre-oxygenation (HFNC, NRM)• Lowest SpO₂ during pre-oxygenation• Name, dosages and timing of pre-medications given
(b) Intubation	
• Time induction agent given, name of induction agent and dose• Time paralytic agent given, name of paralytic agent and dose• Time of successful intubation• Lowest SpO₂ achieved during subsequent intubation attempts (if unsuccessful at 1st attempt)• SpO₂ at the end of intubation• Type of laryngoscope use (direct/ articulating/ video)• Adjunct devices use (e.g. bougie)• Position of intubation• Cormack-Lehane scoring of laryngeal view (state direct or video view)• Intubator speciality and level of experience (by post-graduate year)• Supervision by EM specialist (yes/no)• Peri-intubation adverse events: hypotension, hypertension, tachycardia, bradycardia, regurgitation, aspiration, cardiac arrhythmia, cardiac arrest during RSI, oropharynx or dental trauma

(c) Clinical outcomes	
Length of stay in ICUAs in secondary endpoints
(d) Difficult airway features	
Reduced neck mobility or on C collarMallampati scoreMouth openingThyromental distanceAirway obstructionFacial trauma (if not severe enough to preclude recruitment as per exclusion criteria)Blood or vomitus in airway
(e) Others	
Demographics (age, gender, ethnicity, body mass index)Comorbid conditions (congestive cardiac failure, ischemic heart disease, atrial fibrillation, chronic renal disease, chronic obstructive pulmonary disease, asthma, obstructive sleep apnoea, diabetes, previous head and neck radiation, head and neck mass or infection, upper gastrointestinal bleeding)Pre-intubation vital signs (temperature, heart rate, systolic BP, diastolic BP, mean arterial pressure, Glasgow Coma Scale)Quick SOFA score at triage and prior to pre-oxygenationCXR findingsIndication for intubationVasopressor use

Only the index ED visit is included in the study. There will be no repeat visits. Patients' clinical outcomes as per secondary endpoints will be followed up electronically from the Computerised Patients' Support System (CPSS-2)

8. STATISTICAL CONSIDERATION

8.1 Sample size calculation

Based on our preliminary data and previous studies, we anticipate a standard deviation of 14% in lowest SpO₂. Enrolment of **184 patients** (92 patients in each of control and intervention groups) will provide statistical power of 80% (with a two-sided α of 0.05) to detect a 6% difference in lowest SpO₂, allowing for a 5% dropout.

8.2 General approach for statistical analysis

The primary analysis will be an intention-to-treat analysis, comparing the primary outcome of lowest SpO₂ achieved between two groups. Descriptive statistics of lowest SpO₂ (e.g. mean, standard deviation, median and interquartile range) will be reported for each group. Comparison of mean (or median) lowest SpO₂ between groups will be made using two-sample *t*-test or non-parametric test as appropriate. 95% confidence intervals of difference in lowest SpO₂ will be provided. Categorical data will be compared using the Fisher's exact test. We will use linear and logistic regression to adjust our findings if there are important differences between the study arms that might confound the results.

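### Section 8.2 adjusts only if the arms look different; a pre-specified adjustment for starting SpO₂, already collected, is the better rule

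*Protocol*

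**What the plan says.** Section 8.2 of the protocol sets out the main comparison: "The primary analysis will be an intention-to-treat analysis, comparing the primary outcome of lowest SpO₂ achieved between two groups". The method is unadjusted; the comparison of means or medians "between groups will be made using two-sample *t*-test or non-parametric test as appropriate".

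The section closes with a rule for covariates. Linear and logistic regression will be used to "adjust our findings if there are important differences between the study arms that might confound the results". It names no covariate, does not define an important difference, and does not say which result leads if the adjusted and unadjusted ones disagree.

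Section 7(a) lists among the data collected "SpO₂ at beginning and end of pre-oxygenation (i.e. prior to induction", and also "Lowest SpO₂ during pre-oxygenation". It does not say whether the first reading is taken before or after the allocated device is put on.

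For the sample size, Section 8.1 states that "we anticipate a standard deviation of 14% in lowest SpO₂". It plans 92 patients per arm for 80% power to detect a 6-point difference at two-sided 0.05, with 5% dropout.

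**The concern.** Randomisation makes any baseline difference a chance event. A covariate earns its place because it predicts the outcome, and that can be decided before any data are seen. Choosing it because the arms turned out to differ has two drawbacks, even if the choice is limited to variables related to outcome:

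- Whether an adjusted result exists, and what it adjusts for, depends on the data.
- A strong predictor that happens to be balanced is ignored, although adjusting for it would still narrow the confidence interval.

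Starting SpO₂ is the obvious candidate, being the same measurement as the primary endpoint taken a few minutes earlier. Under the stated rule it is used only if it looks unbalanced.

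Precision is what is at stake, not validity. The protocol itself states the trigger, so an analysis plan that follows the protocol inherits it.

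**Working it through.** **Inputs from Section 8.1.** SD 14 points, difference 6 points, two-sided α 0.05, power 80%, dropout 5%, 92 per arm. Allocation is 1:1 (Section 4.1).

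**Assumed input.** r, the within-arm correlation between starting and lowest SpO₂, is not in the protocol. The range used is 0.2 to 0.5.

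**Step 1: reproduce the plan's figure.** With the noncentral t distribution, power is 79.8% at 86 per arm and 80.3% at 87, so 87 evaluable per arm are needed. Then 87/0.95 = 91.6, which gives 92 per arm and 184 in total. The stated sample size is correct for an unadjusted t-test.

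**Step 2: planned adjustment at 87 per arm.**

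- Residual SD = 14·√(1 − r²)
- Standard error = residual SD·√(2/87)
- Degrees of freedom = 174 − 3 = 171 (172 unadjusted)
- Half-width = t(0.975)·standard error, with t(0.975) = 1.974

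For example, at r = 0.3 the residual SD is 14·√0.91 = 13.36, the standard error is 13.36·0.1516 = 2.025, and the half-width is 1.974·2.025 = 4.00. The noncentrality is 6/2.025 = 2.963, which gives power of 83.8%.

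| r (assumed) | Residual SD | Power | 95% CI half-width (points) | Evaluable n per arm for 80% power |
|---|---|---|---|---|
| unadjusted | 14.00 | 80.3% | 4.19 | 87 |
| 0.2 | 13.72 | 81.8% | 4.11 | 84 |
| 0.3 | 13.36 | 83.8% | 4.00 | 79 |
| 0.4 | 12.83 | 86.6% | 3.84 | 73 |
| 0.5 | 12.12 | 90.1% | 3.63 | 66 |

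**Step 3: what the imbalance rule recovers.** The protocol gives no threshold, so two were assumed. The adjusted result is taken to replace the unadjusted one when the rule fires. The figures come from a normal simulation with 60,000 trials per r.

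| Rule | How often it adjusts | Power at r = 0.2 / 0.3 / 0.4 / 0.5 | Type I error |
|---|---|---|---|
| Always adjust | 100% | 81.7 / 83.7 / 86.4 / 89.9% | nominal |
| Only if starting SpO₂ differs at p<0.05 | 5% | 80.4 / 80.7 / 80.9 / 81.2% | 5.0 / 4.7 / 4.6 / 4.3% |
| Only if it differs by more than 0.2 SD | 19% | 80.6 / 81.3 / 82.2 / 83.2% | 4.8 / 4.5 / 4.2 / 3.7% |

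The conditional rule gains little and is slightly conservative. If the adjusted result is only supportive, primary power stays at 80.3%.

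**Step 4: does the 100% ceiling remove the gain?** Both readings were simulated as normal, rounded and capped at 100 (40,000 trials). Assumptions: control mean 80, observed SD 14, difference 6; starting SpO₂ with mean 96 and SD 6 before capping. The model used HC3 robust standard errors.

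| Quantity | Underlying r = 0.2 | 0.3 | 0.4 | 0.5 |
|---|---|---|---|---|
| Observed r after capping | 0.18 | 0.28 | 0.37 | 0.47 |
| Adjusted power | 80.6% | 82.6% | 85.2% | 88.5% |
| Adjusted power, control mean 84 | 81.0% | 82.7% | 84.9% | 87.9% |
| Adjusted power, 5% of starting values missing, filled with the overall mean (control mean 80) | 80.6% | 82.2% | 84.8% | 88.0% |

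With control mean 80, the t-test had 79.9 to 80.2% power, and type I error of the adjusted model was 4.8 to 4.9%. Most of the gain survives once r is about 0.3 or more.

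**The case against.** The strongest reply is that nothing here is invalid. The unadjusted test holds its error rate and the sample size is right. The natural reading of Section 8.2 may also be that regression is supportive only, in which case the trigger costs the primary test no power. All of that stands. It leaves the rule for the adjusted result still dependent on chance.

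The second reply is that r may be low. The outcome follows three minutes of pre-oxygenation, and Section 2.2 expects saturation above 95% by then, which compresses starting differences. Section 5.2 also excludes "Patients requiring non-invasive positive pressure ventilation", and the scale stops at 100%. By the Step 2 formula, power is only 80.6% at r = 0.1 and 81.1% at r = 0.15. This too stands: the upper end of the range is not a forecast. At low r, however, adjustment costs one degree of freedom and loses practically nothing.

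The third reply is that Section 8.2 already allows a rank test, which can do well on skewed data. In one simulation with gamma-distributed desaturation, the rank test had about 85% power, and the adjusted linear model overtook it only above an observed r of about 0.3. That result depends on the assumed shape, and the rank test does not target the mean difference on which Section 8.1 is built.

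A fourth reply is that the beginning of pre-oxygenation is plain enough as a time point. It probably is, but the device goes on at that moment, and one clause would settle it. Missing-value rules and standard-error methods can fairly be left to an analysis plan. The trigger cannot, because the protocol states it.

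**Conclusion.** The point holds as an improvement that should be made, not as an error that undermines the trial. The trigger in Section 8.2 is a poor rule, and a better one uses data already being collected. The gain depends on an unknown r: negligible at 0.2 or below (80.3% to at most 81.8%), useful from about 0.3 (83.8%, half-width 4.00 against 4.19), and substantial if r reaches 0.5 (90.1%, 3.63). These figures assume SD 14, a 6-point difference and 87 evaluable per arm. Those for the imbalance rule also rest on assumed thresholds and on the adjusted result replacing the unadjusted one. Type I error is not inflated, and the sample size need not change. Confidence is medium because r cannot be checked from the protocol.

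**What to change.** In Section 8.2:

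- State the primary analysis as a linear model of lowest SpO₂ on arm and SpO₂ at the beginning of pre-oxygenation, fitted whatever the observed balance. Report the adjusted mean difference with a 95% CI from robust or bootstrap standard errors.
- Keep the present unadjusted comparison as a sensitivity analysis.
- Delete the condition about important differences between arms.
- Add a simple rule for a missing starting value, for example the overall mean of both arms combined.

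In Section 7(a), state that the starting SpO₂ is recorded before the allocated device is applied. Use no later SpO₂ (end of pre-oxygenation, or lowest during it) as a covariate: those readings are taken on treatment, and adjusting for them could remove part of the effect.

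The cost is a few sentences in Section 8.2, one clarification in Section 7(a) and one degree of freedom. No new data item and no extra patients are needed.

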9. DATA HANDLING AND RECORD KEEPING

The Research Electronic Data Capture (REDCap) system will be used and maintained at SCRI's secure server. Authorised personnel will be assigned user IDs and passwords to gain access to the database. Entered data will be systematically checked by built-in edit checks.

The study participant's information and research data will be securely stored at the dedicated research computers in the NUH and NTFGH Emergency Departments for internal use during the study. The research computers are password protected and located in the Emergency Department administrative offices which are only accessible to authorised personnel by card access. Individual participants and their research data will be identified by a unique study identification number. Patients' identifiers and research data will be stored separately.

10. **CONFLICT OF INTEREST**

The PI and co-investigators declare no conflict of interests.

11. **REFERENCES**

4. Weingart SD. Preoxygenation, reoxygenation, and delayed sequence intubation in the emergency department. *J Emerg Med.* 2011;40(6):661-667.
